## **2.3 Potential Risks and Benefits**

### **2.3.1 Potential Risks**

This is the first clinical study of SAR440894 in humans. Nonclinical toxicology of SAR440894 is presented in [Section 2.1](#). Although no significant risks to humans are anticipated due to the absence of human target, renal toxicity was observed in the mouse toxicity study consisting of adverse renal tubular and interstitial inflammation (not dose-related in terms of incidence or severity) at all doses. Based on the low incidence of findings in all treatment groups, their lack of a clear dose/exposure-related trend in terms of incidence/severity, and the preserved functionality of the organ (no increases in blood urea nitrogen and creatinine) levels, these findings are considered doubtful. While no clear mechanism of toxicity was identified in mice, a potential risk in humans remains.

---

The NHP study demonstrated a mild increase in total urine protein/creatinine ratio at 5 and 15 mg/kg, and a mild to moderate increase in urine albumin/creatinine ratio in males at 15 and 45 mg/kg. At 45 mg/kg, males also had a mild increase in incidence and severity of hematuria/hemoglobinuria. There were no renal microscopic changes observed in the cynomolgus monkey. Test item related changes observed in the urine were considered to be not adverse based on the 1) absence of a dose relationship, 2) the absence of morphological changes in the kidneys or urinary bladders (glomerular damage was ruled out), and 3) the transient effects (no changes were observed after 5 weeks of washout period). The NOAEL was considered to be the top dose of 45 mg/kg, with a Day 15 mean AUClast of 159,000 µg·h/mL and 153,000 µg·h/mL for males and females, respectively.

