**Table 7-1: Clinical Laboratory Evaluations**

Hematology	Chemistry	Urinalysis
	Pregnancy test (serum or urine) Calcium Alkaline phosphatase Bilirubin, direct Albumin Protein, total Estimated glomerular filtration rate*** Follicle stimulating hormone Cystatin-C Creatinine Clearance	the sample should be further analyzed with urine chemistry and microscopy.^^^ Urinalysis will be repeated as necessary for menstruating females.
Coagulation	Drugs of Abuse (Urine) and Alcohol Testing**	Serology Screen
Activated partial thromboplastin time  Prothrombin time  International normalized ratio	Cannabinoids Amphetamines Barbiturates Cocaine Opiates including Methadone Benzodiazepines Phencyclidine Cotinine Breathalyzer (alcohol)	Hepatitis B surface antigen Hepatitis C antibody Human immunodeficiency virus 1 and 2 antibody with antigen CHIKV IgG and IgM antibody

Any lab value may be repeated if felt erroneous due to laboratory error.

\*Values outside the acceptable limits at Screening only are exclusionary with exception of total bilirubin for which ULN values will be allowed at Screening and Day -1/Baseline provided the AST and ALT are within normal limits.

\*\*Values outside the acceptable limits at Screening and Day -1 are exclusionary.

\*\*\*Values for creatinine results that Grade 1 or higher at Screening and Day -1 prior to Protocol Version 11.0 were exclusionary. With Protocol Version 11.0, creatinine is not an exclusionary criterion, instead subjects should have a calculated eGFR using the CKD-EPI of  $\geq 90 \text{ mL/min}/1.73\text{m}^2$  to be enrolled in the study.

+For hemoglobin; a lower limit within 0.5 g/dL of the LLN is allowable at Screening.

++For AST/ALT; results are exclusionary if Screening results are  $1.5 \times \text{ULN}$  or if assessed as CS by the site PI.

---

^Urine abnormalities in menstruating females will trigger repeat urinalysis within the next 14 days, either at a scheduled study visit or via unscheduled study visit following cessation of menses. Urine abnormalities in females attributable to menstruation will not be considered AEs.

^^Urine protein-to-creatinine ratio will be calculated at Screening and Day -1.

^^^Repeat urine collection if cellular elements in the microscopic exam indicate the participant did not successfully follow clean catch instructions.

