#### **4.5.1. Safety Variables**

The following safety endpoints will be assessed:

- Chemistry (CHEM), Hematology (HEM), Urinalysis (UA), and Coagulation (COAG) clinical laboratory result safety parameters will be collected according to the schedule of study procedures in [Table 2](#). The following parameters will be measured:
  - CHEM parameters: alanine aminotransferase (ALT), aspartate aminotransferase (AST), creatinine, total bilirubin, sodium, potassium, bicarbonate, glucose, blood urea nitrogen

(BUN), calcium, alkaline phosphatase (AP), direct bilirubin, albumin, total protein, estimated glomerular filtration rate (eGFR), and Cystatin-C.

- HEM parameters: hemoglobin (HGB), platelet count, white blood cell (WBC) count, hematocrit (HCT), red blood cell (RBC) count, basophil count, eosinophil count, lymphocyte count, monocyte count, and neutrophil count.
- COAG parameters: activated partial thromboplastin time (APTT), prothrombin time (PT), and international normalized ratio (INR).
- UA parameters: protein, occult blood, ketones, leukocyte esterase, glucose, bilirubin, nitrites, urobilinogen, WBC, and urine RBC.
  - UA will first be performed by urine dipstick testing. If any abnormal value is observed on the urine dipstick test, then urine microscopy will be performed, and the results will supersede those of the dipstick UA.
- Vital signs (VS) parameters will be collected according to the schedule in **Table 2**. The following parameters will be measured:
  - Resting (measured after lying supine for at least 5 minutes) temperature, heart rate, systolic blood pressure (SBP), diastolic blood pressure (DBP), and respiratory rate
- ECG parameters will be collected according to the schedule in **Table 2**. The following parameters will be measured:
  - PR interval, QRS duration, QT interval, QT corrected for heart rate by Fridericia's cube root (QTcF) correction, RR interval, and ventricular rate.
    - Triplicate ECGs with 10-second rhythm strips will be obtained within a 60-minute period prior to dosing and within approximately 15 minutes after dosing is complete, separated by at least 1 minute.
    - Single, standard 12-lead safety ECGs will also be obtained.
    - If any significant changes are observed, triplicate ECG tracings, approximately 2 minutes apart, should be recorded and repeated hourly until cessation of the abnormality. Significant changes are defined as
      - Any significant change in rate or rhythm as determined by the site PI

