The sort order for hematology parameters will be as follows: hemoglobin, WBC, lymphocytes, neutrophils, eosinophils, platelets, hematocrit, RBC, basophils, and monocytes.

The sort order for coagulation parameters will be as follows: APTT, prothrombin time, and INR.

The sort order for urinalysis parameters will be as follows: urine protein, urine glucose, bilirubin, nitrite, occult blood, urine WBC, urine RBC, urobilinogen, ketones, and leukocyte esterase.

- All chemistry results, including at unscheduled visits, will be presented in [Listing 15](#). Abnormal chemistry results, including ONR and Grade 1 or higher results, will be presented in [Table 62](#) for participants enrolled prior to Protocol v11.0 and in [Table 63](#) for participants who enrolled under Protocol v11.0.
- All hematology results, including at unscheduled visits, will be presented in [Listing 16](#). Abnormal hematology results, including ONR and Grade 1 or higher results, will be presented in [Table 64](#) for participants enrolled prior to Protocol v11.0 and in [Table 65](#) for participants who enrolled under Protocol v11.0.
- All coagulation results, including at unscheduled visits, will be presented in [Listing 17](#). Abnormal coagulation results, including ONR and Grade 1 or higher results, will be presented in [Table 66](#) for participants enrolled prior to Protocol v11.0 and in [Table 67](#) for participants who enrolled under Protocol v11.0.
- All urinalysis results, including at unscheduled visits, will be presented in [Listing 18](#). Abnormal urinalysis results, including ONR and Grade 1 or higher results, will be presented in [Table 68](#) for participants enrolled prior to Protocol v11.0 and in [Table 69](#) for participants who enrolled under Protocol v11.0.

All screening results will be listed for each participant by treatment group and visit. Serology results will be presented in [Listing 19](#), serum  $\beta$ -hCG and FSH pregnancy testing results will be given in [Listing 20](#), and urine toxicology and alcohol results will be presented in [Listing 21](#).

The distribution of laboratory results will be presented by severity, treatment group, and time point.

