Blood (microscopic)—red blood cells per high power field (rbc/hpf)	0 – 3	HI	4 - 10	11 - 50	> 50 and/or gross blood
WBC (microscopic)—white blood cells per high power field (wbc/hpf)	0 – 5	HI	6 - 10	11 - 50	> 50 and/or gross blood
Urobilinogen (mg/dL)	0.2 – 1.0	HI	> ULN – 1.5	1.6 – 2.0	> 2.0
Vital Signs					
Fever (°C) g		HI	38.0 - 38.4	38.5 - 38.9	> 38.9
Fever (°F) g		HI	100.4 - 101.1	101.2 - 102.0	> 102.0
Tachycardia—beats per minute		HI	101 - 115	116 - 130	> 130 or ventricular dysrhythmias

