[Implementation Note: Generate one table for each chemistry parameter. For calculated fields (Mean, SD, Median), decimal place should be the format in which the data were collected + 1 extra place. For Min, Max, decimal place should be in the same format in which the data were collected.]

[Repeat for each Chemistry Laboratory Parameter, number each table separately]

**Table 198: Clinically Significant Graded Urinalysis Results by Maximum Severity Post-Baseline, Parameter, and Treatment Group for Participants in the Safety Population Enrolled Prior to Protocol v11.0**

[Implementation Note: Repeat for the following treatment groups: All Participants, SAR440894 0.3 mg/kg, SAR440894 1 mg/kg, SAR440894 3 mg/kg, SAR440894 10 mg/kg, SAR440894 20 mg/kg, and Placebo.

The table will include the following parameters: Urine Protein, Urine Glucose, Bilirubin, Nitrite, Occult Blood, Urine WBC, Urine RBC, and Urobilinogen.]

Parameter	Treatment Group	N	Mild / Grade 1		Moderate/ Grade 2		Severe/ Grade 3	
			n	%	n	%	n	%
Urine Protein	All Participants	x	x	xx	x	xx	x	xx
	SAR440894 0.3 mg/kg							
	...							
	Placebo							
Urine Glucose	All Participants							
	SAR440894 0.3 mg/kg							
	...							
	Placebo							
Bilirubin	All Participants							
	SAR440894 0.3 mg/kg							
	...							
	Placebo							
...	...							

Notes: Participants are counted once per maximum severity among all clinically significant labs experienced at any time point post baseline, including unscheduled assessments. N = Number of participants in the Safety Population enrolled prior to Protocol v11.0 with available results post-baseline.

**Table 199: Clinically Significant Graded Urinalysis Results by Maximum Severity Post-Baseline, Parameter, and Treatment Group for Participants in the Safety Population Enrolled Under Protocol v11.0**

[Implementation Note: Repeat for the following treatment groups: All Participants, SAR440894 0.3 mg/kg, SAR440894 1 mg/kg, SAR440894 3 mg/kg, SAR440894 10 mg/kg, SAR440894 20 mg/kg, and Placebo.]

The table will include the following parameters: Urine Protein, Urine Glucose, Bilirubin, Nitrite, Occult Blood, Urine WBC, Urine RBC, and Urobilinogen.]

Parameter	Treatment Group	N	Mild / Grade 1		Moderate/ Grade 2		Severe/ Grade 3		Life-threatening/ Grade 4		Death/ Grade 5	
			n	%	n	%	n	%	n	%	n	%
Urine Protein	All Participants	x	x	xx	x	xx	x	xx	x	xx	x	xx
	SAR440894 0.3 mg/kg											
	...											
	Placebo											
Urine Glucose	All Participants											

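### SAP 4.5.1 lets microscopy supersede the dipstick without limit, and before v11.0 a clinically significant positive occult blood with a normal red cell count has no cell in Table 198 or Table 200

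*SAP*

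**What the plan says.** SAP 4.5.1 defines the urinalysis variables as "UA parameters: protein, occult blood, ketones, leukocyte esterase, glucose, bilirubin, nitrites, urobilinogen, WBC, and urine RBC". Occult blood and urine RBC are therefore two parameters. The dipstick comes first. On any abnormal dipstick value, "then urine microscopy will be performed, and the results will supersede those of the dipstick UA". No list says which parameters this covers.

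SAP 9.6 keeps the two apart in its sort order: "urine protein, urine glucose, bilirubin, nitrite, occult blood, urine WBC, urine RBC, urobilinogen, ketones, and leukocyte esterase". It then assigns the outputs:
- Tables 175-190 for graded parameters, with Occult Blood in 183/184 and Urine RBC in 187/188.
- Tables 191-194 for ungraded parameters (ketones and leukocyte esterase).
- Tables 198/199 for graded clinically significant results, and Tables 200/201 for ungraded ones.

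The note to Table 198 names "Urine Protein, Urine Glucose, Bilirubin, Nitrite, Occult Blood, Urine WBC, Urine RBC, and Urobilinogen". The note to Table 200 names ketones and leukocyte esterase only.

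For participants enrolled before v11.0, the grades are in SAP Tables 5 and 6 (Protocol Appendices C and D). Blood in urine is graded only by microscopic red cells per field: 0-3 normal, 4-10 Grade 1, 11-50 Grade 2, above 50 and/or gross blood Grade 3. Urine protein is graded as 1+, 2+ and above 2+.

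Protocol Table 7-1 says that after an abnormal dipstick "the sample should be further analyzed with urine chemistry and microscopy". Note 8 of Protocol Appendix A, repeated under SAP Table 2, calls for a complete urinalysis with microscopy. Neither says that the dipstick result is replaced. SAP Section 15 lists two changes, on creatinine clearance and on which laboratory abnormalities become AEs. This is not one of them.

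**The concern.** A dipstick and a microscope slide measure different things. The microscopy rows in Tables 5 and 6 are counts of red and white cells, while the protein row is a strip scale. An unlimited rule that one supersedes the other can replace a positive chemical result with a normal cell count, or with no value at all.

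Urine findings deserve care in this trial. Protocol 2.1 names the kidney as the target organ in mice and relies on blood and urine markers to monitor it in humans. Protocol 2.3.1 reports raised urine protein and albumin ratios in monkeys and adds: "At 45 mg/kg, males also had a mild increase in incidence and severity of hematuria/hemoglobinuria". Clinically significant change in safety laboratory values is a primary endpoint (SAP 3.2.1), and Tables 198-201 carry it for urinalysis.

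**Working it through.** No figure in the plan bears on this point, so the check applies the SAP's own rules to two illustrative post-dose samples from a participant enrolled before v11.0.

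**Sample 1: dipstick blood positive, 2 red cells per field, no gross blood, judged clinically significant.** It is assumed that a strip can be positive for blood at a normal cell count. The documents do not discuss this.

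| Output | Literal reading: microscopy replaces the dipstick | Narrow reading: microscopy replaces only cell counts |
|---|---|---|
| Urine RBC, Table 187 | normal (2 lies in 0-3) | normal |
| Occult Blood, Table 183 | positive result superseded | outside normal range |
| Any urinalysis parameter, Table 173 | no grade | no grade |
| Clinically significant, graded, Table 198 | no cell | no cell |
| Clinically significant, ungraded, Table 200 | no row | no row |

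The first two rows show what the supersede sentence decides. Read literally, it also prevents any positive dipstick blood from reaching Tables 183/184, because every positive strip triggers its own replacement. The SAP cannot intend both the sentence and those tables.

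The last three rows do not depend on the reading. Tables 5 and 6 have no row for dipstick blood. Table 198 has columns for Grades 1 to 3 only, and its note has no fallback to an outside-normal-range display. Table 200 has that display but no Occult Blood row. Borrowing the microscopic grade for the Occult Blood row does not help, because a count of 0-3 has no grade.

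**Sample 2: dipstick protein 2+.** Tables 5 and 6 make this Grade 2. Read literally, the value gives way to cell counts and no protein value remains to grade in Table 175. On the narrow reading, Grade 2 stands. No other urine protein measure fills the gap after dosing: Protocol Table 7-1 has the protein-to-creatinine ratio calculated at Screening and Day -1, and SAP 4.5.1 does not list it.

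**Size per event.** With six participants on active drug per dose group and no replacements, one missed participant lowers a Table 198 or 200 percentage by 1/6 = 17 points, or by more if only part of the group enrolled before v11.0. In the pooled placebo group of ten it is 1/10 = 10 points.

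**The case against.** The strongest reply is that the SAP plainly means the narrow reading. It lists occult blood separately from urine RBC everywhere, and the notes to Tables 183 and 184 say that an ungraded parameter is shown as within or outside normal range. SAP 9.6 gives the same rule for laboratory results in general. Note 8 under SAP Table 2 speaks of a complete urinalysis, so the superseding results may include a second protein measurement and not only a cell count.

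The result also has other routes into the report. Abnormal urinalysis results go to Tables 68/69 and all results to Listing 18. Table 40 counts participants with a clinically significant laboratory abnormality as recorded on the laboratory eCRF. Before v11.0, all abnormal laboratory findings were AEs (SAP 6.7). Dose escalation rests on AE-based halting rules and committee review (Protocol 8.6.2 and 8.7.2), not on these final tables, and the safety analysis is descriptive.

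Most of this stands. A reader might infer that hemoglobinuria is always analysed as normal, or that the graded tables cannot detect it. The documents do not support that: it follows only from the literal reading, and Tables 183/184 contradict it. Nor do they support linking the rule to a known monkey pattern of positive strips with few cells. Protocol 2.3.1 gives only the joint term, with no strip results or counts, and judges the urine changes not adverse and transient.

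The reply leaves two things unanswered. The narrow reading is nowhere stated, so a programmer must choose. And the fallback written for Tables 183/184 was not written for Table 198.

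**Conclusion.** The concern holds in two parts. First, the supersede sentence is an unlimited operative rule. It conflicts with the SAP's separate Occult Blood and Urine Protein outputs and is an undeclared departure from a protocol that only adds testing. Read literally, it can turn a blood-positive dipstick with 0-3 red cells into a normal result and can remove a gradable protein value. Second, on either reading, a participant enrolled before v11.0 with clinically significant positive occult blood, a normal red cell count and no gross blood has no cell in the parameter-level clinically significant urinalysis tables.

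The consequence is possible undercounting in tables that serve a primary endpoint. How often it would occur cannot be estimated from the documents. The v11.0 counterparts, Tables 199 and 201, depend on CTCAE grading that the documents do not reproduce, so the second part is not claimed for them. Because the listings, Tables 68/69, AE reporting and, on the narrow reading, Tables 183/184 remain, this is a risk to the summary tables and not a demonstrated loss of the renal signal.

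**What to change.** - In SAP 4.5.1, limit the supersede clause to the cellular elements that microscopy measures, RBC and WBC.
- Analyse occult blood, protein, glucose and the other chemical parameters as reported by the dipstick or the complete urinalysis, with microscopic RBC and WBC as separate parameters. If both methods report the same chemical parameter, state which value is used.
- State that positive occult blood without a toxicity grade is shown as outside normal range in Tables 183/184.
- Move or add Occult Blood to Table 200, and to Table 201 if it is also ungraded under v11.0.
- If any replacement of dipstick results is kept, declare it in SAP Section 15.

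A count of participants with positive dipstick blood and a normal red cell count, and a display of occult blood by strip category, are optional.

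The cost is SAP wording and minor programming, with no new sampling. It assumes that the database stores both the dipstick and the microscopy result. The eCRFs are not among the documents, so this should be confirmed first.

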#### 4.5.2. Pharmacokinetics Variables

SAR440894 plasma concentrations will be determined using a validated enzyme-linked immunosorbent assay. PK samples will be analyzed by Aptuit (Verona) Srl. PK sample collections will be performed at the following time points: Baseline pre-infusion (60 to 0 minutes prior to start of infusion), at the completion of the infusion, and at (relative to the end of the infusion), 1, 4, 8, 12, 24, 48, and 72 hours, and on Day  $7 \pm 1$ , Day  $14 \pm 2$ , Day  $28 \pm 4$ , Day  $56 \pm 4$ , Day  $84 \pm 7$ , Day  $112 \pm 7$ , Day  $150 \pm 7$ , and ET (if needed). For blood sample collection, there will be an acceptable window of  $\pm 10$  minutes in the first 8 hours after dosing and  $\pm 30$  minutes between 9 and 72 hours. PK samples at Follow-up visits will be collected during the designated Follow-up window. The “end of infusion” sample should be obtained within 5 minutes of the end of the infusion.

#### 4.5.3. Immunogenicity Variables

ADA in K3EDTA plasma will be assessed by using validated bridging electrochemiluminescence assays for Screening, confirmation, and titration. Immunogenicity samples for ADAs will be analyzed by Aptuit (Verona) Srl. Plasma samples for ADA measurements will be collected pre-infusion (60 to 0 minutes prior to start of infusion), Day  $56 \pm 4$ , Day  $112 \pm 7$ , Day  $150 \pm 7$ , and ET (if necessary).

For immunogenicity assays, a positive result will be defined as a positive screening assay followed by a positive confirmatory assay. A negative result will be defined as a negative screening assay or a positive screening assay followed by a negative confirmatory assay. Treatment-induced ADA is defined as a negative result at baseline and a positive result post-dose. Treatment-boosted ADA is defined as a positive result at both baseline and post-dose, with a 4-fold increase to titer. Pre-existing ADA is defined as a positive result at both baseline and post-dose, but without meeting the definition of treatment-boosted ADA.

## 5. SAMPLE SIZE CONSIDERATIONS

No formal sample-size calculations based on testing a statistical hypothesis were performed. This study plans to randomize 40 participants. The number of participants was selected to allow sufficient evaluation of safety, and PK of the various single dose regimens to be administered in this study and is consistent with standards of practice for Phase 1 studies.

## 6. GENERAL STATISTICAL CONSIDERATIONS

### 6.1. General Principles

Unless otherwise specified, continuous variables will be summarized by the following descriptive statistics: the number of participants with non-missing data included in the analysis (n), mean, standard deviation (SD), median, minimum value (min), and maximum value (max). Summary statistics for discrete data will include frequencies and proportions and may include confidence intervals (CIs) for the proportion. When 95% CIs are given for a proportion, exact (Clopper-Pearson) CIs will be used, unless otherwise specified.

All randomized participants will be included in summaries of participant demographics. The Safety Population will be used for summaries of safety endpoints, the PK Population will be used for summaries of PK endpoints, and the Immunogenicity Population or the Pharmacokinetics – Immunogenicity Subset Population will be used for summaries of immunogenicity endpoints. Denominators for clinical, clinical laboratory, VS, and ECG results at planned study time points will be the number of participants in the Safety Population with available results at the specified time point for that parameter. Denominators for the conceptual “Maximum Severity Post Baseline” time point for clinical, clinical laboratory, VS, and ECG results will be the number of participants with an observed result for the parameter obtained post-dose. Unless otherwise specified, denominators for all other safety endpoints will be the number of participants in the Safety Population. All tables will be annotated with the total population size relevant to that table/group, including any missing observations.

The sort order for listings is indicated in the implementation note for each listing shell. The sort order of treatment groups is given in [Section 3](#). The sort order of clinical laboratory tests, VS, and ECG parameters is described in [Section 9](#).

